#### 1) Xeljanz group: 4000 subjects for safety analysis

· The target sample size is set to be 4000 subjects by adding a certain sample size a) b) of  $\geq 3000$  subjects beginning from the start of registration (3-year observation) to the subsequent number of subjects (6-month observation period). See “6.5 observation period” for more information. However, even if Xeljanz is administered to subjects who do not meet the conditions described in “2. Subjects” for inevitable reason(s), while such subjects will not be included in the above sample size, the request to enroll subjects and complete survey forms will be made for subjects in the Xeljanz group for the sake of all-cases survey.

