### **5.1.2. Comparison of the Xeljanz group and the control group**

- Comparative analysis set

Of the enrolled patients with a scheduled observation period of 3 years, those who were confirmed to treat Xeljanz in the Xeljanz group and a control drug (control drug is MTX, biological agents, DMARDs or immunosuppressive drug) at least once were included in the control group. The patients who apply to a to f in Section 5.1.1 are excluded.

The control group also excludes patients who do not meet the MTX criteria and patients who have been treated with Xeljanz.

- MTX adherent comparative analysis set

The MTX adherent comparative analysis set of the Xeljanz group is the patients who meets the MTX criteria among the new patients of the comparative analysis set.

As for the control group, since the comparative analysis set of the control group is limited to the patients who meet the MTX criteria, the same set is also used as the control group of MTX adherent comparative analysis set.

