### 6.3. Covariates

For both the Xeljanz and control groups, candidate covariates related to the development of malignant tumors and serious infections are shown below.

Covariates	Malignant tumor	Serious infection
Sex	○	○
Age	○	○
Weight	○	○
Stage of rheumatoid arthritis	○	○
Class of rheumatoid arthritis	○	○
Duration or disease	○	○
Past history (infection)	×	○
Past history (malignant tumor)	○	×
Past history (lung disorder)	×	○
Past history (interstitial pneumonia)	×	○
Complication (infection)	×	○
Complication (malignant tumor)	○	×
Complication (hepatitis B)	○	×
Complication (hepatitis C)	○	×
Complication (diabetes mellitus)	×	○
Smoking history	○	○
Family history of malignant tumors (including lymphoma)	○	○
History of MTX use (Within 3 months prior to the start of survey)	○	○
MTX criteria	○	○
History of oral steroid use (Within 3 months prior to the start of survey)	○	○
History of tacrolimus use (Within 3 months prior to the start of survey)	○	○
Past use of biological agents (Within 3 months prior to the start of survey)	○	○

Covariats	Malignant tumor	Serious infection
Initial dose of Xeljanz	○	○
Neutrophil count	○	○
Lymphocyte count	○	○
Prophylactic administration to prevent tuberculosis	×	○
Prophylactic administration to prevent pneumocystis jiroveci pneumonia	×	○
Prophylactic administration to prevent hepatitis B	×	○
DAS28	○	○

○: Applicable, ×: Not applicable

Covariates may be added or removed based on the results of the interim analyses of this survey and newly obtained findings. In that case, this plan will be revised.

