### 8.2.3. Safety Analysis

#### 8.2.3.1. Comparison of Xeljanz group and control group

A comparison of the Xeljanz group and the control group is performed for each of the MTX adherent comparative analysis set and the comparative analysis set. The main analysis set is the MTX adherent comparative analysis set.

The adverse events including corporate evaluation is used for the main analysis, and as a secondary analysis, the analysis of adverse events based only on the doctor's evaluation is also used.

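### In the secondary comparative analysis set the propensity-weighted hazard ratios cannot balance MTX criteria, because only controls are required to meet them

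*SAP*

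**What the plan says.** SAP Section 5.1.2 builds the comparative analysis set from patients with a scheduled 3-year observation. For controls it adds a restriction: "The control group also excludes patients who do not meet the MTX criteria and patients who have been treated with Xeljanz". The Xeljanz arm has no matching restriction. MTX status limits that arm only in the narrower MTX adherent comparative analysis set, which "is the patients who meets the MTX criteria among the new patients of the comparative analysis set". The section then confirms that the limit in the wider set falls on controls, and so uses one control group for both sets: "As for the control group, since the comparative analysis set of the control group is limited to the patients who meet the MTX criteria".

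Xeljanz patients outside the criteria do exist in the survey. Protocol Section 3, item 1, does not count them toward the target of 4000, but "the request to enroll subjects and complete survey forms will be made for subjects in the Xeljanz group for the sake of all-cases survey".

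SAP Section 8.2.3.1 says the comparison "is performed for each of the MTX adherent comparative analysis set and the comparative analysis set", and names the MTX adherent set as the main one. The introduction to the list in Section 6.3 reads: "For both the Xeljanz and control groups, candidate covariates related to the development of malignant tumors and serious infections are shown below". MTX criteria is marked applicable there for both outcomes. Section 8.1.6 puts the Section 6.3 covariates into the propensity score, fitted by logistic regression and by random forests. Section 8.2.3.1.1 defines the weight as Z + θ(1−Z)/(1−θ), with an alternative version that caps large weights. Section 8.2.3.1.2 reuses that weight for serious infections.

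**The concern.** Weighting can balance a covariate only if both groups contain patients at each of its levels. In the wider set the control group has nobody at the level *criteria not met*, and this is by design rather than by chance. A weighted hazard ratio from that set would appear to be adjusted for MTX criteria, since the covariate is on the list, but the difference between the arms would be untouched.

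At stake is how the two sets are read together. A reader will treat agreement or disagreement between the main and the wider set as a robustness check. If patients outside the criteria have a different underlying risk of cancer or serious infection, the wider-set weighted result shifts for that reason alone. The shift could look like a drug effect or hide one.

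**Working it through.** **Context figure.** The plan gives no figure for this point. Its sample-size rationale supplies a rate and a drop-out assumption, and these reproduce. With drop-out rising linearly to 50% at 3 years, mean follow-up is 3 × (1 + 0.5)/2 = 2.25 years, and 4000 × 2.25 × 0.0116 = 104.4, against the stated 104. The simulation below uses that rate and 50% drop-out at 3 years, in exponential form.

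**Step 1: overlap.** In the wider set P(control | criteria not met) = 0, so the true propensity score θ of a non-meeter is 1. In a logistic fit to simulated data of this shape, the MTX coefficient ran off to about 30 to 33 before iteration stopped, and the fitted θ for non-meeters was 1.

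**Step 2: weights.** With Z=1 for Xeljanz, the weight is 1. With Z=0 it is θ/(1−θ). After weighting, non-meeters are still a share p of the Xeljanz arm and 0% of the control arm. This holds for any θ, so random forests cannot change it. The cap acts only on controls, because all Xeljanz weights equal 1.

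**Step 3: size.** Let p be the share of non-meeters in the Xeljanz arm and h their hazard relative to meeters. Suppose the true hazard ratio is 1, events are rare, and everything else is balanced. With r the meeters' rate:

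- Xeljanz arm: (1−p)·r + p·h·r
- weighted control arm: r
- ratio: (1−p) + p·h

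Both p and h are assumptions.

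- p=10%, h=1.5: 0.90 + 0.15 = 1.05
- p=30%, h=1.5: 0.70 + 0.45 = 1.15
- p=30%, h=2: 0.70 + 0.60 = 1.30
- p=30%, h=0.67: 0.70 + 0.20 = 0.90
- any p, h=1: 1.00

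**Step 4: simulation.** The conditions were: true hazard ratio 1; the 4000:2000 ratio scaled up 100-fold; one further confounder; logistic propensity score; the SAP weight; a weighted exponential model standing in for Cox; one run per scenario. The cap was set at the 95th percentile of control weights, which is an assumption because the SAP leaves it open.

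| p | h | Formula | Weighted only | Weighted, capped | Meeters only |
|---|---|---|---|---|---|
| 10% | 1 | 1.00 | 1.002 | 1.014 | 1.003 |
| 10% | 1.5 | 1.05 | 1.063 | 1.075 | 1.013 |
| 30% | 1 | 1.00 | 1.004 | 1.013 | 0.997 |
| 30% | 1.5 | 1.15 | 1.146 | 1.157 | 1.009 |
| 30% | 2 | 1.30 | 1.249 | 1.262 | 0.959 |
| 50% | 2 | 1.50 | 1.462 | 1.477 | 0.979 |

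Run-to-run noise is shared across each row. At p=30%, h=2, for example, 1.249/0.959 = 1.30, which is the formula value. Adding MTX criteria to the weighted outcome model gave the same results as the meeters-only column.

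**Step 5: the other adjusted estimates.** The pooled incidence ratio in Section 8.1.6 is Σ(aᵢPT₀ᵢ/Tᵢ) / Σ(bᵢPT₁ᵢ/Tᵢ). The non-meeting stratum has PT₀ᵢ = 0 and bᵢ = 0, so it adds zero to both sums, and pooling on MTX criteria returns the meeters' ratio. A Cox model that includes MTX criteria gives non-meeters their own coefficient, so the treatment contrast again comes from meeters.

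**The case against.** The strongest reply is that little depends on this. The main set is clean, Section 4 calls all tests exploratory, and two of the three adjusted methods handle the factor correctly. All of that stands and limits the point to one type of estimate in a secondary set.

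Four further replies stand in part.

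- **Further adjustment.** Sections 8.2.3.1.1 and 8.2.3.1.2 add a weighted model with covariates that change the hazard ratio markedly. It removes the bias if MTX criteria is selected, but no threshold is given and selection is not assured.
- **Balance display.** Both sections require proportions and standardised differences before and after weighting. These would show, say, 30% against 0%, so the imbalance would not be hidden. No rule says what follows from seeing it.
- **Candidate list.** The Section 6.3 list may change. It also contains initial dose of Xeljanz, which controls cannot have, so it cannot be applied literally. But dropping MTX criteria from the propensity score would not help: non-meeters would still sit in one arm with weight 1.
- **Redacted text.** Material after Section 8.2.3.1.3 is blacked out. Whether it deals with overlap cannot be judged, and nothing here assumes that it does not.

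A reader might infer that the main comparison is confounded, that MTX criteria adjusts nothing in any analysis, or that the bias must count against Xeljanz. The documents support none of these. Both arms of the main set meet the criteria, so the covariate is merely constant there. The Cox and pooled estimates do use it in the wider set. The direction of bias depends on h, which is not given.

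**Conclusion.** The plan is wrong as written for a secondary estimate: the weighted-only hazard ratios for malignant tumor and serious infection in the comparative analysis set. The lack of overlap follows from the set definitions and needs no assumption beyond the presence of non-meeting Xeljanz patients in that set, which the definition of the narrower set implies.

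Whether it biases the result depends on MTX status, or what goes with it, being prognostic. Section 6.3 presumes this by listing it among "candidate covariates related to the development of malignant tumors and serious infections are shown below". The size is illustrative only. For p from 10% to 50%, the factor runs from 1.05 to 1.25 at h=1.5 and from 1.10 to 1.50 at h=2. At h=0.67 it falls from 0.97 to 0.84, and at h=1 there is no bias. The formula assumes rare events and balance on everything else. Covariate balance under random forests was not tested, though the MTX imbalance itself does not depend on the propensity method.

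**What to change.** In Sections 8.2.3.1.1 and 8.2.3.1.2, compute the propensity score and the weighted hazard ratio only in patients of both groups who meet the MTX criteria, and omit MTX criteria, then constant, from that propensity model.

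If the wider-set weighted estimate is to be kept, fit the propensity score among meeters without this covariate, always include MTX criteria in the weighted outcome model, and state that the contrast comes from meeters only.

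In either case, report non-meeting Xeljanz patients descriptively, with rate and 95% confidence interval. The SAP already reports a non MTX adherent safety set in this way for the key survey items. The Cox and pooled analyses can stay, provided the Cox model includes MTX criteria.

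The cost is SAP wording and minor programming. The wider-set weighted hazard ratio for each outcome will come close to the main-set estimate, differing only by Xeljanz patients who are not new, so it adds less as a second view. The main analysis result does not change.

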## 5.2. Efficacy Analysis Set

- Efficacy Analysis Set

The efficacy analysis set is defined as the safety analysis set excluding patients meeting at least one of the following criteria.

- No results of efficacy evaluation were reported (description in the report: “No efficacy information”)  
Efficacy evaluation to be reported: Tender joint count (TJC), swollen joint count (SJC), patient VAS, physician VAS, ESR, and CRP
- Diseases not investigated in the survey (description in the report: “Disease outside the survey scope”)  
Diseases not investigated in the survey: Patients aged 16 years or younger, patients receiving Xeljanz for conditions other than rheumatoid arthritis

Efficacy in the control group will not be investigated.

- MTX adherent efficacy analysis set

The MTX adherent efficacy analysis set is the patients who meets the MTX criteria among the efficacy analysis set.

The acceptance or rejection of the safety and efficacy analysis se will be examined after treating patients consulted at multiple centers as the same patients. Multi-center consultation patients are patients in which the investigation has been completed and it has been confirmed that multiple identifications have been assigned to the same patient by transfer of hospital or department. Patients in which the investigation is completed and it is confirmed that there is no transfer or department transfer are considered as single-center consultation patients.

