### 6.4 Patient registration

[1] After the date on which the contract for this Surveillance is concluded, the investigator conducting surveillance will complete the registration form provided by Sponsor, and submit the form to Patient Registration Center via FAX.

[Patient Registration Center]

[contact]

Business hours: 9:00 to 17:15 (except for Saturdays, Sundays, National Holidays, and New Year Holidays)

\*FAX transmission after 16:00 will be responded during the following business day.

[2] Definition of start date

(1) Xeljanz group

The date on which administration of Xeljanz begins will be considered the “start date of treatment.” However, for patients participating in the clinical trial, the start date will be considered the date on which administration of the commercially available Xeljanz product begins, and in the case of subjects administered Xeljanz at other medical facilities, it will be the date on which treatment at the physician’s own hospital begins.

(2) Control group

For rheumatoid arthritis patients with poorly controlled disease in spite of continuous use of a methotrexate preparation (MTX) in a dosage exceeding 8 mg/week for 3 months or more, the date on which the change in pharmacotherapy began is regarded as the “start date of surveillance.”

[3] Enrollment method

(1) Xeljanz group

The registration form should be submitted to the Patient Registration Center via FAX in principle no later than 1 week prior to the start of Xeljanz therapy.

If the sponsor has made the judgment that there has been a deviation from the scope of proper use of Xeljanz on the basis of the registration information, this will be checked with the physician in charge of surveillance, and the proper use information will be explained. If any of the patients registered in the control group has been administered Xeljanz during the registration period, the patient will also need to be registered in the Xeljanz group.

(2) Control group

The registration form should be faxed to the Case Registration Center within 2 weeks after surveillance start in the control group.

In principle, case selection in the control group should be performed according to the prescribing conditions for routine medical care under actual use conditions.

Patients to whom any of the following apply will be excluded from candidates for registration in the control group.

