#### **5. ANALYSIS SETS**

##### **5.1. Safety Analysis Set**

###### **5.1.1. Safety analysis of the Xeljanz group**

- Safety analysis set

Of the enrolled patients with a scheduled observation period of 3 years and 6 months, those who have been confirmed to have received Xeljanz at least once are included. However, the following patients will be excluded from the safety analysis set.

- a. No CRF was collected (description in the report: "CRF not collected");
  - b. There was a violation or flaw of the contract (description in the report: "Violation/flaw of contract");
  - c. There was a violation in the enrollment process (description in the report: "Enrollment violation");
  - d. No information on the administration of survey drug was reported (description in the report: "No administration information");
  - e. No information on adverse events was reported (ie., existence or non-existence of adverse events is unidentifiable) - No visits after the initial prescription (description in the report: "No information on adverse events - No re-visits");
  - f. No information on adverse events was reported - Visits conducted after the initial prescription, but no record (description in the report: "No information on adverse events - No record").
- MTX adherent safety analysis set

The MTX adherent safety analysis set is defined as the patients with rheumatoid arthritis who have been poorly controlled if methotrexate (MTX) at a dose of more than 8 mg/week is continuously used for 3 months or longer among the new patients of the safety analysis set, that is described in the "Guidelines for the use of tofacitinib for all patients post-marketing surveillance".

The new patient is defined as the patients in which administration of Xeljanz was started for the first time after the registration of this surveillance in the Xeljanz group. In addition, the target patients with rheumatoid arthritis are 16 years old or older, and patients under 16 years old are excluded.

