#### 8.2.4. Efficacy Analysis

Analysis is performed for each of the MTX adherent efficacy analysis set and the efficacy analysis set. The main analysis target set is the MTX adherent efficacy analysis set.

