## 11. APPENDICES

### 11.1. Appendix 1: Details of Data Extraction

#### 11.1.1. Definition of Visit Timing

Day 1: In the Xeljanz group, the oldest initiation date in the status of administration of Xeljanz.

In the control group, the oldest initiation date in the status of drug administration.

Visit timing	Evaluation item	Definition [acceptance range]
Before the initiation of administration	Laboratory test Blood pressure Efficacy observation items	= 'Date of assessment' - 'Date Day 1' + 1 = [-30 - 1] Target date = 1
1 month after the initiation of administration	Laboratory test Blood pressure Efficacy observation items	= 'Date of assessment' - 'Date Day 1' + 1 = [2 - 62] Target date = 31
3 month after the initiation of administration	Laboratory test Blood pressure Efficacy observation items	= 'Date of assessment' – 'Date Day 1' + 1 = [63- 138] Target date=92
6 month after the initiation of administration	Laboratory test Blood pressure Efficacy observation items	= 'Date of assessment' – 'Date Day 1' + 1 = [139- 230] Target date=184
9 month after the initiation of administration	Laboratory test Blood pressure Efficacy observation items	= 'Date of assessment' – 'Date Day 1' + 1 = [231- 321] Target date=275
12 month after the initiation of administration	Laboratory test Blood pressure Efficacy observation items	= 'Date of assessment' – 'Date Day 1' + 1 = [322- 412] Target date=366
15 month after the initiation of administration	Laboratory test Blood pressure Efficacy observation items	= 'Date of assessment' – 'Date Day 1' + 1 = [413- 503] Target date=457
18 month after the initiation of administration	Laboratory test Blood pressure Efficacy observation items	= 'Date of assessment' – 'Date Day 1' + 1 = [504-595] Target date=549

Visit timing	Evaluation item	Definition [acceptance range]
21 month after the initiation of administration	Laboratory test Blood pressure Efficacy observation items	= 'Date of assessment' – 'Date Day 1' + 1 = [596- 686] Target date=640
24 month after the initiation of administration	Laboratory test Blood pressure Efficacy observation items	= 'Date of assessment' – 'Date Day 1' + 1 = [687- 777] Target date=731
27 month after the initiation of administration	Laboratory test Blood pressure Efficacy observation items	= 'Date of assessment' – 'Date Day 1' + 1 = [778- 868] Target date=822

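### The main efficacy set (SAP 5.2) lacks the new-patient restriction of the parallel sets, so some patients can enter with a baseline measured on Xeljanz

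*SAP*

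**What the plan says.** SAP 8.2.4 names the set on which the efficacy conclusions rest: "The main analysis target set is the MTX adherent efficacy analysis set". The full efficacy set is the other set analysed.

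SAP 5.2 builds the main set in two steps. First, "The efficacy analysis set is defined as the safety analysis set excluding patients meeting at least one of the following criteria"; the criteria are absence of efficacy data and a disease or age outside the survey's scope. Second, "The MTX adherent efficacy analysis set is the patients who meets the MTX criteria among the efficacy analysis set".

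The two sibling sets carry one more condition. The MTX adherent safety set in SAP 5.1.1 is taken "among the new patients of the safety analysis set", and the Xeljanz arm of the comparative version in SAP 5.1.2 is "the patients who meets the MTX criteria among the new patients of the comparative analysis set". SAP 5.1.1 defines a new patient as one in whom "administration of Xeljanz was started for the first time after the registration of this surveillance".

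On start dates, Protocol 6.4 says that for clinical-trial patients "the start date will be considered the date on which administration of the commercially available Xeljanz product begins". For patients given Xeljanz elsewhere, it is the start of treatment at the registering physician's own hospital. SAP 11.1.1 sets Day 1 as follows: "In the Xeljanz group, the oldest initiation date in the status of administration of Xeljanz". The pre-treatment efficacy window is Day -30 to Day 1.

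**The concern.** The efficacy outcomes in SAP 8.2.4 are the change since Xeljanz was started (SDAI, CDAI, DAS28 and their components), EULAR response, and remission and disease activity at each visit. Month 6 SDAI remission is also tested across subgroups. Change and EULAR response need a baseline taken before the drug, and remission is read as the result of starting it.

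A patient who comes from a clinical study already on Xeljanz has a baseline that reflects earlier treatment. If that patient has already responded, little further improvement is left to record. If already in remission, the patient counts as a Month 6 success that did not arise in this survey. Baseline SDAI is itself a subgroup factor in SAP 11.1.4, with a lowest category of 3.3 or below. Responders already on treatment would tend to collect there and affect that comparison.

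There is also a mismatch of populations. SAP 8.2.2 tabulates background by MTX criteria within new patients, so those tables would describe a different group from the one behind the main efficacy results.

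**Working it through.** The plan gives no figure on this point to reproduce. The check is a comparison of definitions, followed by arithmetic for scale.

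**1. Conditions on the Xeljanz patients in each set**

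| Set | SAP section | MTX criteria | New patients only |
|---|---|---|---|
| MTX adherent safety | 5.1.1 | yes | yes |
| MTX adherent comparative | 5.1.2 | yes | yes |
| MTX adherent efficacy (main) | 5.2 | yes | no |

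**2. Is the restriction implied?** No. SAP 5.1.2 states the MTX criteria and new-patient status as two separate conditions. The efficacy set descends from the full safety set, not from the MTX adherent safety set. None of the exclusions in 5.1.1 (a to f) or 5.2 concerns earlier Xeljanz use.

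**3. Who can enter?** Protocol 7.1 records three registration categories for the Xeljanz group: newly prescribed, from a clinical study, and from another facility. The last two enter if they meet the MTX criteria.

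**4. Which baseline do they get?**
- Clinical-study patients: the clock starts with the commercial product. If they pass to it directly from study drug, the Day -30 to Day 1 window falls on treatment.
- Transfers: SAP 5.2 decides set membership after treating confirmed multi-centre patients as one patient, and Day 1 is the oldest initiation date. For a merged record this may recover the true start. The problem remains for transfers whose earlier records are not merged.

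**5. Is efficacy split by patient category?** SAP 8.2.2 does so for background in the efficacy set, and SAP 8.2.3.2 does so for adverse drug reactions. The visible text of SAP 8.2.4, 5.4 and 11.1.4 does not do so for efficacy results.

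**6. Scale.** Let f be the share of already-treated patients in the main set and r their mean change divided by that of new patients. Both are assumptions; the documents give neither.

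Observed mean change ÷ new-patient mean change = 1 − f(1 − r)

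Shift in remission (percentage points) = f × (remission in already-treated − remission in new patients)

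| f | Ratio, r = 0 | Ratio, r = 0.5 | Shift if gap is +20 points | Shift if gap is −10 points |
|---|---|---|---|---|
| 1% | 0.99 | 0.995 | +0.2 | −0.1 |
| 5% | 0.95 | 0.975 | +1.0 | −0.5 |
| 10% | 0.90 | 0.95 | +2.0 | −1.0 |
| 20% | 0.80 | 0.90 | +4.0 | −2.0 |

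Example for f = 10%, r = 0 and an assumed new-patient SDAI change of −15: 0.90 × (−15) = −13.5. With assumed remission of 20% in new and 40% in already-treated patients: 0.90 × 20% + 0.10 × 40% = 22%.

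Limiting the set to new patients makes f = 0, and both effects vanish.

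**The case against.** The case on the other side has real weight.

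- **Transfers.** A reader might infer that every patient from another hospital has an on-treatment baseline. The documents do not support that. The survey covers all prescribing sites (Protocol 4), so many transfers should have a first-hospital record, and merging together with the oldest initiation date may restore their true start. This stands and narrows the point to clinical-study patients and unmerged transfers.
- **Missing new-patient result.** A reader might infer that none is planned anywhere. Text is redacted just before SAP 8.2.4 and after 8.2.4.3, so one can say only that the visible plan specifies none.
- **Small share.** To enter, these patients must have had poor control despite MTX above 8 mg/week for at least 3 months, with that history after February 23, 2011 (Protocol 2). This may exclude many clinical-study patients. It stands; f could be near the bottom of the range or below it.
- **Drafting slip.** SAP 8.2.2 nests the MTX criteria within new patients for the efficacy set as well, so the omission in 5.2 may be unintended. That is plausible, but a programmer following 5.2 as written would still include these patients.
- **Limited consequence.** Efficacy is single-arm and tests are exploratory (SAP 4). Protocol 8.2 asks for all evaluable patients with at least one administration, so including earlier users breaches nothing in the protocol. This stands. It bears on the weight of the point, not on whether a change from an on-treatment baseline measures response to starting Xeljanz.

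**Conclusion.** The definition in SAP 5.2 differs from those in 5.1.1 and 5.1.2 with no reason given, and as written it admits clinical-study patients and unmerged transfers whose baseline can be on-treatment. This rests on the text alone and is firm.

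The effect is less certain. Attenuation of the mean change is expected, because patients kept on the drug have probably already responded. A reader might go further and take their change to be zero by construction, but nothing in the definition forces that, and r could lie above 0. Remission may move either way. Upward is more likely, since patients still on treatment are selected for response or tolerance.

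The size cannot be derived. The upper end, a mean change 20% too small, needs both f = 20% and no further change in those patients. At f = 1% the loss is 1% or less for r between 0 and 1. A material distortion is therefore possible but not shown. The point is worth acting on because the inconsistency is certain and the repair is cheap.

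**What to change.** In SAP 5.2, define the MTX adherent efficacy analysis set as the patients who meet the MTX criteria among new patients in the efficacy analysis set, in line with 5.1.1 and 5.1.2. State that new-patient status for merged multi-centre patients is judged on the merged record. In SAP 8.2.4, show clinical-study and other-hospital patients separately, with their numbers, so that f becomes visible.

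SAP version 10.0 was written after database release, so the change should be disclosed as made after release, and the result under the current definition should be reported alongside.

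The cost is a few words and one extra set of tables. Patient category is already recorded at registration, so no new data are needed. The downside is a somewhat smaller main efficacy set.
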